### **12.3 Descriptive Statistics and Exploratory Data Analysis**

Demographic and other baseline data including disease characteristics will be listed and summarized. Categorical data will be presented as frequencies and percentages. For continuous data, mean, standard deviation, median, 25th and 75th percentiles will be presented.

### **12.4 Primary Analysis**

#### **12.4.1 Analysis Population**

The analysis population will include all patients who initiated the RT and chemotherapy regimen (intent-to-treat). Patients who withdraw from the study prior to start of treatment will be replaced.

#### **12.4.2. Analysis Plan**

Our primary analysis will be the calculation of the cCR rate, defined as the percentage of patients who achieved cCR in the analysis population. The cCR and the two-sided 95% Clopper-Pearson (exact) confidence interval will be calculated for the analysis population.

### **12.5 Secondary Analysis**

#### **12.5.1 Analysis Population**

For the secondary outcome of local regrowth rate, the analysis population will include all patients managed with organ preservation approach. For the secondary outcomes of

toxicity, DFS, colostomy-free survival, OS and HRQOL, the analysis population will be the same set of patients included for the primary analysis.

### **12.5.2 Analysis Plan**

For the toxicity outcome, we will calculate the proportion of patients meeting our definition of toxicity. In addition, we will present the frequency and percent of other adverse events reported in the study.

Local regrowth rate will be calculated as the proportion of patients with local regrowth based on the secondary analysis population. The local regrowth rate and its 95% confidence interval will be calculated.

Disease-free survival is defined as the time from start of RT therapy to date of progression or death due to any cause. If a subject is not known to have progressed or died, then DFS will be censored at the latest date the subject was known to be alive or disease-free (on or before the cut-off date). The DFS distribution will be estimated using the Kaplan-Meier method, and the Kaplan-Meier curves, medians and 95% confidence intervals of the medians will be presented.

Colostomy-free survival distribution will be estimated using the Kaplan-Meier method, and the Kaplan-Meier curves, medians and 95% confidence intervals of the medians will be presented.

OS is defined as the time from start of RT therapy to date of death due to any cause. If a subject is not known to have died, then OS will be censored at the latest date the subject was known to be alive (on or before the study end date). The OS distribution will be estimated using the Kaplan-Meier method, and the Kaplan-Meier curves, medians and 95% confidence intervals of the medians will be presented.

For the HRQOL measures, we will calculate the mean and standard deviations of each of the individual indices at baseline and every 3 months during the duration of the study; we will graphically depict scores at each time point. In addition, we will calculate the difference of the QoL scores at the baseline, time of cCR, and last follow up date and report summary statistics.

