#### **4.4 Criteria for Removal from Study**

Patients will receive treatment and follow-up as per Study Calendar until death or end of the study period, whichever occurs first.

A patient has the right to withdraw from the study at any time for any reason without prejudice to his/her future medical care by the physician or at the institution, and the study PI has the right to withdraw a patient from study if they do not follow the treatment recommendations provided by the study investigators.

In the absence of treatment delays, treatment with study agents may span a period of

approximately 4 months (including RT and chemotherapy). Patients may discontinue treatment for any of the following reasons:

- Disease progression,
- Intercurrent illness that prevents further administration of treatment,
- Withdrawal due to patient non-compliance,
- Withdrawal due to patient request,
- Study termination, and/or
- General or specific changes in the patient's condition which render the patient unsuitable for further treatment in the judgment of the investigator or treating physician.

If a patient does not return for a scheduled visit, every effort should be made to contact him/her. In any such circumstance, every effort should be made to document the subject's outcome. Patients who leave Stanford or continue their care elsewhere will be contacted every 6 months by telephone, email, or mail. After three failed attempts to reach the patient, either via mail or telephone or a combination of the two, contact will cease and the patient will be considered lost to follow-up.

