### 10.2 Secondary Outcome Measures

- Toxicity at least possibly attributed to treatment, graded using CTCAE v5 criteria and assessed up to 3 months after completion of RT and chemotherapy, expressed as a number and proportion without dispersion.
- 2-year local regrowth rate where local regrowth is defined as the presence of adenocarcinoma within the rectal wall or within the mesorectum confirmed by pathology, expressed as a percentage with its 95% confidence interval.
- DFS defined as the time from the start date of RT to the date of the first documented progression or death due to any cause assessed up to 2 years after completion of chemotherapy. Patients will be censored at the last date of follow-up if lost to follow-up prior to two years, expressed as a median with interquartile range.
- Colostomy-free survival defined as the time from the start date of RT to the date of colostomy or death due to any cause assessed up to 2 years after completion of

chemotherapy, expressed as a median with interquartile range. Patients will be censored at the last date of follow-up if lost to follow-up prior to two years.

- OS defined as death from any cause from start date of RT until death, study completion, or loss to follow-up, whichever occurs first. This will be reported as median survival time with interquartile range.

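### The 2-year local regrowth rate is planned as a crude proportion with no rule for follow-up that ends before month 24, so early loss understates it slightly

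*Combined protocol and SAP*

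**What the plan says.** Section 10.2 lists as a secondary outcome the "2-year local regrowth rate where local regrowth is defined as the presence of adenocarcinoma within the rectal wall" or mesorectum, confirmed by pathology, to be given as a percentage with a 95% confidence interval.

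Section 12.5.1 sets the denominator: "For the secondary outcome of local regrowth rate, the analysis population will include all patients managed with organ preservation approach". Section 12.5.2 sets the estimator: "Local regrowth rate will be calculated as the proportion of patients with local regrowth based on the secondary analysis population". It then adds: "The local regrowth rate and its 95% confidence interval will be calculated". These sections give regrowth no time origin, month-24 cut-off, censoring rule or interval method.

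The neighbouring endpoints are treated differently:

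- **DFS and colostomy-free survival.** Section 10.2 says: "Patients will be censored at the last date of follow-up if lost to follow-up prior to two years".
- **Estimation.** Section 12.5.2 says: "The DFS distribution will be estimated using the Kaplan-Meier method". It uses the same method for colostomy-free survival and OS, and gives a censoring rule for OS.
- **Interval for cCR.** Section 12.4.2 names the "two-sided 95% Clopper-Pearson (exact) confidence interval".

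Section 4.4 foresees withdrawal and loss to follow-up. For a missed visit it also says: "In any such circumstance, every effort should be made to document" the outcome.

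**The concern.** A 2-year rate is a statement about risk by a fixed time. Events divided by everyone who entered surveillance equals that risk only if each patient is either observed to month 24 or has documented regrowth. A patient last scoped at month 3 and then lost stays in the denominator as a non-event, although regrowth between months 3 and 24 was never excluded. The error goes one way, towards a lower rate.

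Regrowth is the outcome that shows whether observation holds after a good response. Section 1.2 names it first among the cancer outcomes for organ-preservation patients. As planned, a reader could not tell how many patients in the denominator had been assessed through month 24.

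**Working it through.** **No planned figure to reproduce.** The documents give no target, precision or loss rate for regrowth. The only sample-size figure is the Simon design for cCR in section 12.6.2. An exact calculation for 3/17 then 11/37 gives type I error 0.0948 and power 0.9033, consistent with the stated 0.1 and 0.9. From the cCR rates in that section, organ-preservation patients number roughly 37 x 0.2 = 7.4 to 37 x 0.4 = 14.8, so about 7 to 15.

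**Assumptions.** None of these is a planning value in the documents:

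- constant regrowth and loss hazards, independent of each other;
- loss by month 24 (L) of 10%, 20% or 30%;
- true 2-year regrowth risk (R) of 2.8%, 25% or 35%. The 2.8% is the 2 of 71 quoted in section 2.2.1 for a watch-and-wait series after a different regimen. The other two are illustrative.

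**Formula.** Let lambda = -ln(1-R)/24 and mu = -ln(1-L)/24. If no regrowth is documented after loss, the expected crude proportion is

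c0 = [lambda/(lambda+mu)] x [1 - exp(-24(lambda+mu))].

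If a share q of post-loss regrowth is documented, it is c0 + q(R - c0).

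**One cell in full** (R = 25%, L = 20%): lambda = 0.01199 and mu = 0.00930, so the first factor is 0.563. The second is 1 - 0.75 x 0.80 = 0.40. The product is 22.5%.

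| True 2-year risk | 10% loss | 20% loss | 30% loss |
|---|---|---|---|
| 2.8%, q = 0 | 2.7% | 2.5% | 2.4% |
| 25%, q = 0 | 23.8% | 22.5% | 21.2% |
| 25%, q = 0.5 | 24.4% | 23.8% | 23.1% |
| 35%, q = 0 | 33.3% | 31.6% | 29.8% |
| 35%, q = 0.5 | 34.2% | 33.3% | 32.4% |

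At q = 1 there is no bias.

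**In patients.** The largest average shift is 15 x (0.350 - 0.298) = 0.78 patient. At a true 2.8% it stays below 0.07 patient, even with 15 patients and 30% loss.

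**Worked example.** Take 11 patients with regrowth at months 6, 9 and 15, two lost, and six followed to month 24. The crude rate is 3/11 = 27.3% (exact 95% CI 6.0-61.0%). There are no competing events here, so the Aalen-Johansen estimate is one minus the product over risk sets:

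- lost at months 12 and 18: 1 - (10/11)(9/10)(7/8) = 28.4% (log-log CI 6.7-55.7%);
- both lost at month 3: 1 - (8/9)(7/8)(6/7) = 33.3% (7.8-62.3%);
- both last scoped at month 3, but telephone or virtual contact to month 21 counted as follow-up: 1 - (10/11)(9/10)(8/9) = 27.3%, the crude figure again.

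The last line shows that the censoring date matters as much as the estimator.

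**Visit dates.** In the first case, suppose a fourth regrowth is found at the month-24 visit. On nominal months the estimate is 1 - 0.7159 x 5/6 = 40.3%. If that visit is dated two weeks late, after the other five completers are censored, the estimate becomes 100%.

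**The case against.** Several points against this are sound.

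- **Surveillance is intensive.** The Study Calendar schedules endoscopy every 3 months and pelvic MRI at months 3, 6, 12, 18 and 24. A reader might infer from the footnotes on virtual follow-up and deferred DRE that regrowth need not be looked for. The documents do not say so: neither footnote cancels endoscopy or MRI.
- **The timeline fits.** Section 3.4 puts primary completion at 60 months and study completion at 84, which leaves 24 months. This limits administrative truncation, so what remains is true loss or withdrawal.
- **Regrowth found elsewhere is not excluded.** Section 4.4 asks for the outcome to be documented, and outside pathology would meet the section 10.2 definition. Suspected regrowth on surveillance goes to tissue confirmation (section 4.2.5), so confirmed cases already count. It would be wrong to read the plan as missing all regrowth managed elsewhere. But section 4.4 governs data collection and does not tell the analyst how to handle a patient whose status stays unknown.
- **The denominator is specified and reproducible.** That is true, but the convention is correct for a 2-year risk only when follow-up is complete.
- **Cumulative incidence can err the other way.** If outside regrowth is captured but outside clear examinations are not, simulation with half of post-loss regrowth documented gives 26.3% at a true 25% with 20% loss, against a crude 23.8%. At a true 35% with 30% loss it gives 37.4%, against 32.4%. When both kinds of report are retrieved, the estimates are 25.1% and 35.0%. This is a good reason to show both measures and to seek both kinds of report.

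**Conclusion.** The gap is real and small. The endpoint's name promises a 2-year risk; its formula gives that risk only with complete 24-month assessment. For patients who are lost or withdraw without documented regrowth it is biased downward: by 1.2 to 5.2 points at assumed true risks of 25-35% and 10-30% loss, and by at most about 0.4 points at 2.8%. These biases halve if half of post-loss regrowth is documented and vanish if all of it is. All of this rests on assumed loss rates, regrowth risks and constant hazards. With 7 to 15 patients, sampling error far exceeds the bias.

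A reader might go further and conclude that the crude rate is invalid, or that the trial's conclusion is at risk. Neither follows. Local regrowth is descriptive and secondary, and the acceptance rule in section 12.7 uses only cCR and toxicity. N = 37 is unaffected.

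Whether near-complete responders belong in this population is a separate clarification and not part of the bias.

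**What to change.** In section 12.5.2:

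1. Report the 24-month cumulative incidence of pathology-confirmed local regrowth from Time 0 as set in section 4.2.5 (Aalen-Johansen), with death and TME without regrowth as competing events. State the interval method, for example log-log, or exact binomial if there are no events.
2. Censor patients without regrowth at their last endoscopy or pelvic MRI, not at a telephone or virtual contact. Assign visits inside the calendar's 2-week window to their nominal month.
3. Count regrowth documented outside the protocol, and request outside clear endoscopy and MRI reports as well as pathology.
4. Keep the crude proportion alongside with a Clopper-Pearson interval, and report the number with a complete 24-month assessment.

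Separately, add a sentence to section 12.5.1 saying whether near-complete responders under observation are in the regrowth population. The Synopsis and section 2.3 tie organ preservation to cCR, while sections 4.2 and 4.2.5 leave room for others. These passages need reconciling.

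The cost is SAP wording, standard code and some record requests, using visits already in the Study Calendar. The downsides are a slightly less favourable figure, a wide interval and possibly informative censoring, which the count of complete assessments helps a reader judge.

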## PROTOCOL SYNOPSIS

TITLE	Phase II Trial of Organ Preservation Program Using Short-Course Radiation and FOLFOXIRI for Rectal Cancer (SHORT-FOX)
STUDY PHASE	Phase II
INDICATION	Treatment
INVESTIGATIONAL PRODUCT OR PROCEDURE	Organ preservation approach using short course radiation followed by FOLFOXIRI for patients with non-metastatic, >T2N0 or low T2N0 rectal cancer
PRIMARY OBJECTIVE	To assess clinical complete response of an organ preservation approach using short course radiation followed by intensified chemotherapy
SECONDARY OBJECTIVES	To assess safety in all enrolled patients, local regrowth rate and other cancer specific outcomes (disease-free survival, colostomy-free survival and overall survival), longitudinal health-related quality of life of this organ preservation approach
TREATMENT SUMMARY	Patients will undergo short-course radiation followed by 4 months of FOLFOXIRI. Those who achieve a clinical complete response will be considered for organ preservation approach. All other patients will receive standard of care total mesorectal excision (TME).
SAMPLE SIZE	37 patients
STATISTICAL CONSIDERATIONS	
Sample Size Calculation: We plan to use an optimal Simon 2 stage design and enroll 37 patients with an interim analysis at 17 patients for futility.
 
Primary Endpoint: Clinical complete response assessed 8 (+/-4) weeks after completion of chemotherapy.
 
Secondary Endpoints: Toxicity, local regrowth rate, disease-free survival, colostomy-free survival, and overall survival assessed until study completion.
 
Exploratory Endpoint: Health-related quality of life assessed until study completion.

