#### **Study Completion:**

The study will reach study completion 84 months from the time the study opens to accrual.

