#### **4.2.5 Follow-Up Schedule (Time 0 = assessment of primary outcome)**

Patients who achieve cCR and are candidates for organ preservation per multidisciplinary review will undergo surveillance per protocol schedule. If tumor shows near complete response, patient may continue to be observed until the next evaluable timepoint.

Additional scans and/or other tests may be performed and will be based on the clinical judgment of the treating physician.

Patients who are not candidates for organ preservation will proceed with TME. These patients will not proceed with the organ preservation surveillance schedule and instead be followed for cancer-specific outcomes (disease-free survival, colostomy-free survival and overall survival) per standard of care as directed by the treating physician. They will be assessed for AEs and health-related quality of life per Study Calendar.

For patients who achieve cCR and are on surveillance schedule, if suspicion of local regrowth (non-resolving residual abnormality that appears to increase in size or appears more suspicious in appearance or palpation, or imaging characteristics concerning for progression), patient will undergo a biopsy or a transanal full-thickness excision (TAE) if deemed appropriate to confirm. If biopsy is positive, patients will be managed per standard of care as directed by the treating physician.

Patients who pursue treatment for disease progression while on study will continue to be followed for OS, but discontinue routine AE assessment and QOLs, and follow-up with their treating physicians per standard of care.

After 2 years, all patients who initiated treatment on the protocol will be off study and followed for survival only. In general, patients who opt for organ preservation are recommended to continue to undergo surveillance years 3-5 as per below:

Recommend surveillance off study during years 3-5:

- Every 3-6 months
  - Exam and sigmoidoscopy
- Every 6 months
  - MRI pelvis and CT chest every 6 months

Follow-up PET/CTs or PET/MRI (preferred) are optional at any follow-up point, as per treating physician.

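### Section 12.5.2 in effect censors disease-free survival (DFS) by the overall survival rule, and its cut-off date is undefined while the synopsis and 10.2 give different horizons

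*Combined protocol and SAP*

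**What the plan says.** All references are to the combined protocol and SAP.

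- **DFS censoring, 12.5.2.** Where no DFS event has been recorded, the rule reads: "then DFS will be censored at the latest date the subject was known to be alive or disease-free (on or before the cut-off date").
- **OS censoring, 12.5.2.** "OS will be censored at the latest date the subject was known to be alive (on or before the study end date").
- **DFS window, 10.2.** The event is "first documented progression or death due to any cause assessed up to 2 years after completion of chemotherapy". The censoring sentence is "Patients will be censored at the last date of follow-up if lost to follow-up prior to two years", with no link to a disease evaluation.
- **DFS window, synopsis.** The secondary endpoints include "disease-free survival, colostomy-free survival, and overall survival assessed until study completion". Section 3.4 dates that: "The study will reach study completion 84 months from the time the study opens to accrual".
- **Follow-up, 4.2.5, with Time 0 at the primary outcome assessment.** "After 2 years, all patients who initiated treatment on the protocol will be off study and followed for survival only".
- **Patients who move away, 4.4.** "Patients who leave Stanford or continue their care elsewhere will be contacted every 6 months by telephone, email, or mail".

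The starting point (start of RT) and the event (progression or death) agree between 10.2 and 12.5.2. Only the censoring date and the end of the window are at issue.

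**The concern.** A DFS time should be censored when the patient was last known to be free of disease. If it is censored when the patient was last known to be alive, a patient whose disease is no longer evaluated stays in the risk set as event-free. Any progression in that period goes unrecorded, and only a later death can count.

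The protocol itself creates such a period, because 4.2.5 moves every treated patient to survival-only follow-up after two years. Whether that time enters DFS depends on a cut-off date that the documents do not define, with two different horizons stated elsewhere. Two analysts following the text could therefore produce different DFS curves for a named secondary outcome. The error from the censoring rule runs in one direction only, upward.

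**Working it through.** The documents give no DFS rate or event count, so there is no plan figure to reproduce. The check has a logical part, a date part and an illustration.

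**1. The censoring date.** Let A be the last date known alive and F the last date known disease-free. A patient disease-free on a date is alive on it, so F ≤ A and the later of the two is always A. The disease-free alternative in 12.5.2 therefore never changes the date. What remains is the OS rule, apart from a differently named bound.

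**2. Direction.** Each Kaplan-Meier factor is 1 − d/n. With the same recorded events d, later censoring can only keep n the same or raise it, so the curve is equal or higher.

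**3. Where each window ends, from RT start.** From 4.2 and 4.2.2: about 1 week of RT, a gap of 2-4 weeks and 16 weeks of chemotherapy (8 cycles of 14 days), without delays. Time 0 is 4-12 weeks later.

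| Source | Calculation | End of DFS window |
|---|---|---|
| 10.2 | 19-21 weeks ÷ 4.345 + 24 | about 28.4-28.8 months |
| 4.2.5 protocol follow-up | 23-33 weeks ÷ 4.345 + 24 | about 29.3-31.6 months |
| Synopsis with 3.4 | month 84 from opening | up to about 84 months for the first patient |
| 12.5.2 | cut-off date | not defined |

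**4. Illustration.** These inputs are assumptions, not document figures:
- true two-year DFS S of 70% or 80%, with constant hazard λ = −ln(S)/24 (0.01486 or 0.00930 per month);
- 10-20% of DFS events are deaths without progression (share s);
- median survival after progression of 18-48 months, with μ = ln 2/median.

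For a patient event-free when disease evaluation stops, survival u months later is OS(u) = e^(−λu) + λ(1−s)·[e^(−μu) − e^(−λu)]/(λ−μ).

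*(a) Cut-off at study completion, no disease status recorded after T = 29.3-31.6 months.* The reported curve is e^(−λT)·OS(t−T). At t = 48:

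| S | True | Lowest cell (T = 31.6, s = 20%, median 18) | Highest cell (T = 29.3, s = 10%, median 48) | Error |
|---|---|---|---|---|
| 70% | 0.70² = 49.0% | 0.6252 × 0.9104 = 56.9% | 0.647 × 0.9475 = 61.3% | +7.9 to +12.3 |
| 80% | 0.80² = 64.0% | 0.7454 × 0.9418 = 70.2% | 0.7615 × 0.9658 = 73.5% | +6.2 to +9.5 |

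The standard error at 48 months with 37 patients is about 8-9 points. In the 70% case the median reads 62-84 months against a true 46.6. In the 80% case it reads at least 95.5 months, so it is not reached by month 84, against a true 74.6.

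*(b) Two-year horizon.* A share q of 10-30% loses disease evaluation at a uniform time U within 24 months while vital status stays known. The error at 24 months is q·(g − S), where g is the average of e^(−λU)·OS(24−U) over U.
- S = 70%: g = 0.783-0.813. Error from 0.1 × 0.083 = +0.8 to 0.3 × 0.113 = +3.4 points. Standard error √(0.7 × 0.3/37) = 7.5.
- S = 80%: g = 0.857-0.877. Error from 0.1 × 0.057 = +0.6 to 0.3 × 0.077 = +2.3 points. Standard error √(0.8 × 0.2/37) = 6.6.

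The true medians of 46.6 and 74.6 months lie beyond a horizon of about 29 months, so the median is not reached under either censoring rule.

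**The case against.** The strongest reply is that the large figures hang on one loose line. The synopsis applies study completion to five endpoints together, including toxicity, which 10.2 limits to three months after treatment. It reads as a generic summary, not as a deliberate 84-month DFS horizon. If the cut-off date means the 10.2 limit, then 10.2 and 12.5.2 agree, scenario (a) disappears and only the synopsis is out of line. This stands, and it is why (a) is only an upper illustration. It does not supply the missing definition.

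Second, contact outside the clinic is not necessarily limited to vital status. Section 4.4 asks for every effort to document the patient's outcome. Section 4.2.5 follows patients after total mesorectal excision (TME) for cancer-specific outcomes, DFS among them. Quality-of-life forms fall due at months when surveillance visits also take place. This stands too: where disease status is recorded, the rule does no harm. Within two years, a reader might infer that all remote contacts inflate DFS, and the documents do not support that.

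Third, a reader might infer that the strict 10.2 limit biases DFS because the month-24 visit, counted from Time 0, falls after it. A fixed horizon does not bias the curve before it. Which two-year limit to choose is a preference.

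Fourth, the authors may have meant alive *and* disease-free. That is plausible, but no section says so.

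**Conclusion.** The point holds as a drafting fault with a one-sided effect. Section 12.5.2 gives DFS the OS censoring date, and the documents do not name one end for the DFS window.

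- **Cut-off past two years:** about +6 to +12 points at 48 months. This assumes constant hazard, two-year DFS of 70-80%, the stated post-progression survival, and no disease status recorded in survival-only follow-up.
- **10.2 limit:** about +0.6 to +3.4 points at 24 months if 10-30% of patients lose disease evaluation, which is below sampling error. With complete evaluation to the horizon there is no material bias.

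The textual conflict is certain; the size is not, because the documents supply none of the inputs. A reader might infer that the reported DFS median will be badly wrong. That needs the long horizon, since under 10.2 the median is not reached either way. Nor does the trial's conclusion depend on this: DFS is descriptive, with no test or threshold, and the cCR and toxicity decision rules do not use it. It should be corrected before analysis.

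**What to change.** 1. In 12.5.2, replace the DFS censoring sentence with wording such as: *Patients without progression or death are censored at their last disease evaluation documenting no progression, whether at a protocol visit or as a standard-of-care evaluation after TME. Contacts that establish vital status alone do not extend DFS.*
2. Define the cut-off date as a single horizon, no later than the end of the two-year protocol follow-up, and state the origin from which the two years run.
3. Use the same DFS text in the synopsis, 10.2 and 12.5.2. In 10.2 it replaces the reference to last follow-up.

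**Cost.** A few sentences in three places, plus abstraction of evaluation dates after TME, which the Study Calendar does not list. DFS may look slightly less favourable. The new rule can also err slightly low, by under about 2 points at 24 months in illustration (b), because deaths after the last evaluation still count as events while unassessed survivors leave the risk set. No visit or treatment changes.
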